2.0 Objectives

Aim 1 (Phase 1). Refine a treatment protocol for preoperative education and training and postoperative application of VR-BF in children and adolescents undergoing surgery. We will collect qualitative feedback (regarding content, usability, perceived benefits) via questionnaires and a semi-structured interview and sensitivity to change of key physiological parameters (heartrate variability, respiratory rate) from 12-32 patients (12-18 years) undergoing surgery anticipated to cause moderate to severe pain. Purposive sampling will be used to obtain a representative sample of a broad patient population. Treatment protocol refinement using iterative methodology will allow us to define the trial protocol, including frequency and duration of **(1a)** preoperative education and training and **(1b)** postoperative administration of VR-BF.

Feasibility and Acceptability of Technology-Based Interventions in the Perioperative Setting

Aim 2 (Phase 2). Conduct a pilot randomized controlled trial to assess the feasibility and acceptability of perioperative use of VR-BF in children and adolescents undergoing surgery. Seventy children and adolescents (12-18 years) scheduled for surgeries anticipated to cause moderate to severe pain will be randomized to receive VR-BF or active control (commercially available *Manage My Pain* application). *Manage My Pain* is engaging but lacks specific instruction in behavior change techniques, a key feature of VR-BF. It is included as the control arm to confirm appropriateness for use in the future efficacy trial. Specifically, (2a) Feasibility will be assessed by rates of study recruitment, enrollment and randomization, retention, and adherence. Target goals will be set at 80% for each assessment. (2b) Acceptability will be assessed by treatment/study burden, satisfaction, treatment credibility, and tolerability. It is essential that both treatment arms are feasible and acceptable for use in an efficacy trial.

Our central hypothesis is that preoperative education and training combined with independent, self-directed, repeated postoperative use of VR-BF will be feasible and acceptable in this population. This proposal addresses key components necessary for the design of a large-scale, clinical efficacy trial.

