Data Collection (Table 3). **Feasibility.** *Recruitment:* The number of patients screened per month will be recorded and assessed for eligibility; reasons for ineligibility will be recorded. If 80% of patients do not meet criteria, we will adjust criteria as necessary. *Enrollment and randomization:* Enrollment and randomization will be defined as agreeing to participate in the study and being willing to be randomized. We will record the number of eligible patients approached and enrolled each month. We will collect reasons for refusal to enroll, including unwillingness to be randomized. If rates are not maintained at 80%, we will adjust strategies accordingly. *Retention:* We will define retention as the number of patients who complete the study by participation in the last study visit for both arms. We will collect reasons for dropout. If $\geq 80\%$ retention is not maintained, we will evaluate reasons for dropout. *Adherence:* We will define adherence to preoperative training as completion of the education and training session with the study team and completion of $\geq 5/7$ daily sessions. Adherence to postoperative VR-BF/app use will be defined as completion of $\geq 5/7$ daily sessions. Our target will be $\geq 80\%$ completion. We will collect reasons for failure.

Questionnaires and the semi-structured interview will also assess feasibility using measures based in the literature.¹¹⁹

Acceptability. Treatment/Study

Burden: Burden will be assessed by collecting data on daily log completion, data from questionnaires, and participation in the interview. We will collect reasons for drop out to better understand treatment and study burden.

	Measures	Definition	Benchmarks	Additional Data
Feasibility	Recruitment	Number of patients screened per month	$\geq 80\%$ will meet eligibility criteria	Reasons for not meeting criteria
	Enrollment and randomization	Number of patients approached who agree to enroll in the study and be randomized to a treatment arm	$\geq 80\%$ of those approached will agree to enroll and be randomized	Reasons for refusal, including unwillingness to be randomized
	Retention	Number of participants who complete the study as defined by participation in the last study visit	$\geq 80\%$ retention	Reasons for dropout
	Adherence	Treatment-specific adherence	$\geq 80\%$ will complete ≥ 1 session per day for $\geq 5/7$ days (preop) and ≥ 1 session per day (postop)	Reasons for failure

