Requirements. A signed consent form will be obtained from the participant. For participants who cannot consent for themselves, such as those below the legal age, a parent, legal guardian, or person with power of attorney, must sign the consent form; additionally, the participant's assent must also be obtained if he or she is able to understand the nature, significance, and risks/benefits associated with the study. The consent form will describe the purpose of the study, the procedures to be followed, and the risks and benefits of participation. A copy of the signed consent form will be given to the participant, parent, or legal guardian, and this fact will be documented in the participant's record.

Procedure. The approved, HIPAA compliant informed consent/assent will be provided to the study participant and the parents for review. The consent will be completed through the Research Electronic Data Capture (REDCap) database or on paper forms (if eConsent is unavailable at the time of consent). After allowing adequate time for review, the participant and parents will have the opportunity to ask questions and receive answers. When all questions have been answered, the consent and/or assent will be signed, and a signed copy will be provided to the participant and parents. This will all be conducted before any study measures interventions are undertaken.

Phone Consent. Due to needing subjects to begin study participation prior to surgery, we are requesting permission to consent by phone in order to have time to have subjects be trained on the technology prior to the scheduled surgery. Potential subjects may schedule surgery over the phone or at an in-person visit however subjects who are in person may not be available for approach due time constraints or already being overwhelmed with information regarding the surgery.

Documentation of Ineligibility. Screen failures will be documented on the source worksheets with the supporting data accompanying the eligibility screening form. Documentation of ineligibility or non-participation for each consented participant will be maintained in an electronic database (e.g., REDCap). Reports detailing the reasons for screen-failure and non-participation of eligible participants will be reviewed by the study team to determine if the exclusion criteria require revision in order to make the study accessible to families and study participants.

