Feasibility. We will calculate descriptive data on 1) How many patients are screened per month; 2) Percentage of patients meeting eligibility criteria; 3) Percentage of eligible patients approached, enrolled, and randomized; 4) Percentage of patients completing Phase 2; and 5) Percentage of patients adhering to preoperative education and postoperative application of VR-BF as defined in the study measures. For each measure, the rates, variances, and two-sided 95% confidence interval (CI) will be reported. Each CI will be examined to determine if the hypothesized value of 80% is contained within the interval. This data will also be used to generate a diagram of participant flow. Because this is a feasibility study, we will not conduct statistical tests on the clinical outcomes collected for exploratory purposes (pain and anxiety ratings, opioid use). We will analyze this data using descriptive measures stratified by treatment arm. **Acceptability.** We will calculate descriptive data on 1) Treatment/study burden: number and percentage of patients completing all study measures; 2) Tolerability: number and percentage of patients experiencing AEs; and 3) Any quantitative data of satisfaction and treatment credibility from questionnaires and semi-structured interviews. For each of these measures, the rates, variances, and two-sided 95% CI will be reported. The CI for treatment/study burden will be examined to determine if the hypothesized value of 80% is contained within the interval. Qualitative treatment credibility and parent/patient satisfaction data will be assessed qualitatively as described below.

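### The eligibility trigger in section 6.0 is inverted against its own 80% benchmark; secondarily, the tolerability benchmark concerns serious AEs but the listed analysis counts any AE

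*Combined protocol and SAP*

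**What the plan says.** **Eligibility.** Under Recruitment in section 6.0 (Aim 2, Data Collection) the action rule is "If 80% of patients do not meet criteria, we will adjust criteria as necessary". Table 3, in the same section, sets the recruitment benchmark as at least 80% who "will meet eligibility criteria". The two rules that follow run the other way from the eligibility sentence. For enrollment and randomization: "If rates are not maintained at 80%, we will adjust strategies accordingly". For retention, if at least 80% "retention is not maintained, we will evaluate reasons for dropout". Section 2.0 says of the feasibility measures, recruitment included, "Target goals will be set at 80% for each assessment". Section 17.0 reports "Percentage of patients meeting eligibility criteria" and adds "Each CI will be examined to determine if the hypothesized value of 80% is contained within the interval". Section 13.0 provides for reports of screen-failure reasons to be "reviewed by the study team to determine if the exclusion criteria require revision", without a number.

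**Tolerability.** Table 3 defines the measure as the number and percent of patients with an adverse event (AE) of any kind, but its benchmark is under 1% with a serious AE. The text below the table expects under 1% for adverse events generally, and grades them as minor or moderate/severe. The acceptability analysis in section 17.0 lists only the any-AE number and percentage. Section 15.0 says that serious AEs are reported by routine channels. Section 18.0 refers to a separate monitoring plan, which is not among the documents.

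**The concern.** The eligibility sentence is the only numeric rule for acting on eligibility while the trial runs, and it states the complement of the benchmark. A team that follows it as written has no numeric prompt to revisit the criteria until eligibility is 60 percentage points below target. A defined population with clear eligibility criteria is one of the deliverables of Aim 2 (section 17.0, anticipated outcomes), so the rule should respond to an ordinary miss.

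For tolerability, the listed output is not the quantity that Table 3 benchmarks. Section 15.0 names motion sickness as the greatest risk, so a non-serious event is the kind the plan itself foresees. A single such event would give an any-AE percentage above 1%, with no listed serious-AE percentage beside it to compare with the benchmark.

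**Working it through.** **1. The two eligibility thresholds.**
- Literal trigger: 80% ineligible, so eligible share = 100% − 80% = 20% or less.
- Benchmark missed: eligible share below 80%, so more than 20% ineligible.
- Silent range: above 20% and below 80% eligible.

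**2. The plan's pilot figure (section 3.0).** 95/550 = 17.3% ineligible, which reproduces the stated 17%. Eligible: 455/550 = 82.7%, exact 95% CI 79.3% to 85.8%. The interval straddles the 80% benchmark and lies far from 20%. The pilot took ages 8–18 and approached patients after surgery; this trial takes ages 12–18 before surgery, so the rate may differ.

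**3. What the gap means in counts.** With 70 enrolled and 80% enrollment, and assuming that every eligible patient is approached, the screening load at the benchmark is 70/(0.80 × 0.80) = 109.4, or 110.
- Benchmark: 0.80 × 110 = 88 eligible needed, so it is missed from 23 ineligible upward.
- Literal trigger: 0.80 × 110 = 88 ineligible.
- Silent: 23 to 87 ineligible. At the pilot rate one expects 0.173 × 110 = 19.

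**4. Monthly or cumulative rate.** Section 6.0 records screening by month and anticipates one recruit per week, or 52/12 = 4.33 per month. On the same assumption, 4.33/(0.80 × 0.80) = 6.8, so about 6–7 are screened per month. The chance that a month shows under 80% eligible when the true rate is p = 0.827:
- n = 6: P(X ≤ 4) = 1 − p⁶ − 6p⁵(1 − p) = 1 − 0.321 − 0.402 = 0.28.
- n = 7: P(X ≤ 5) = 1 − p⁷ − 7p⁶(1 − p) = 1 − 0.265 − 0.388 = 0.35.

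A month-by-month rule would therefore fire by chance in roughly 28–35% of months. A single look at the cumulative rate after 110 screened has P(X ≤ 87) = 0.19: lower, though not negligible, because the pilot rate is so close to 80%.

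**5. Tolerability.** Section 17.0 assesses acceptability for each arm, so n = 35 (70 randomized 1:1).
- One event: 1/35 = 2.9% in an arm (exact 95% CI 0.07% to 14.9%), or 1/70 = 1.4% overall. Under 1% therefore means zero events.
- Zero events, exact two-sided 95% upper limit = 1 − 0.025^(1/n): 10.0% at n = 35 and 5.1% at n = 70.

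**6. Sample size.** 56/0.80 = 70, and the exact CI width at n = 56 and 80% is 0.223, so the stated 70 reproduces to rounding. Neither point affects it.

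**The case against.** The strongest reply is that the intended eligibility rule is plain. Table 3, the 80% targets in section 2.0, the two neighbouring rules and the check against 80% in section 17.0 all point the same way. A missed benchmark would also be seen, because the rate is reported, and the screen-failure review in section 13.0 needs no threshold. All of that stands, and it makes this a probable slip. It does not correct the sentence, which remains the only numeric action rule for eligibility and disagrees with everything around it.

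The pilot's 82.7% also argues against any large shortfall. That stands too. A reader might infer that the trial is set to let eligibility fall to 20%, with several times the screening load; the documents give no basis for expecting this. The point concerns a modest miss.

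On tolerability, a reader might infer that the serious-AE rate will never be known, or that safety monitoring is deficient. The documents do not support either. Serious AEs are reported under section 15.0, the monitoring plan in section 18.0 may supply the count, section 17.0 ties no decision to the 1% mark, and both pilots reported no adverse effects. What remains is that the supplied analysis text does not list the benchmarked quantity.

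**Conclusion.** The eligibility trigger is wrong as written. Literally it acts at 20% eligible or fewer, against a benchmark of at least 80%, and is silent across the 60 points between. The finding rests on the text alone. That a modest miss is the plausible case rests on the pilot rate carrying over approximately to a narrower age range recruited before surgery.

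The tolerability mismatch is real but secondary: definition, expectation and listed analysis refer to any AE, and the benchmark to serious AEs. At 35 per arm the 1% mark can be met only by zero events, and zero events does not show a true rate below 1%. Both are matters of internal consistency.

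**What to change.** - **Section 6.0, Recruitment:** reword the rule so that criteria are reconsidered when fewer than 80% of screened patients, counted cumulatively, are eligible. Keep the existing discretion over whether to change them, since even the cumulative rate can dip below 80% by chance.
- **Section 6.0, Table 3 and the tolerability text:** make the definition, the benchmark and the under-1% expectation refer to the same kind of event, or mark the text figure as an expectation only.
- **Section 17.0, Acceptability:** add the number and percentage of patients with a serious AE, by arm, with exact 95% CI, beside the any-AE figures. Label the comparison with 1% as descriptive.

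Cost: a few sentences and one table row, with no change in sample size. The one possible addition is a serious yes/no field on the case report form. Section 6.0 grades severity rather than seriousness, and lists adverse events among items that may be collected.

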7.0 Data and Specimen Banking*

NA

8.0 Sharing of Results with Subjects*

NA

9.0 Study Timelines*

Each individual subject will have a participation period of no more than 3 months depending on timing of initial preoperative visit. Patients will be approached before surgery, have a study visit in person or virtual before surgery, and participate in practice sessions for 1 week prior to surgery. They will participate in the study during their hospitalization and may opt to continue participation for up to 2 weeks following hospital discharge.

We anticipate a total of up to 3 years to fully enroll all study subjects.

We anticipate completion of primary analysis by the end of year 3 (12/24).

10.0 Inclusion and Exclusion Criteria*

Screening: Surgery patient lists and the operating room schedules will be screened for eligible patients based upon basic eligibility criteria such as age and surgical procedure.

Inclusion/Exclusion:

Inclusion criteria. Patients will be eligible if they are:

- Between the ages of 12 and 18 years, inclusive
- Able to read, understand, and speak English
- Scheduled to undergo surgery at NCH anticipated to cause moderate to severe pain with staying at least 1 night in the hospital post-op.

Feasibility and Acceptability of Technology-Based Interventions in the Perioperative Setting

- Require postoperative pain management by the Acute Pain Service
- Own or have access to a mobile device or computer for study participation

Exclusion criteria. Patients will be ineligible if they:

- Are less than 12 years of age or older than 18 years of age
- Are non-English speaking
- Have a history of significant developmental delay, psychiatric conditions associated with hallucinations or delusions, or significant neurological disease, especially epilepsy/seizure disorder
- Have a history of significant motion sickness
- Have a history of chronic pain
- Are chronically using opioids or benzodiazepines for the management of pain
- Are actively experiencing nausea or vomiting
- Have any conditions that preclude their ability to use the virtual reality (VR) headset, such as craniofacial abnormalities or surgeries of the head and neck
- Previous participation in this study

Children (ages 12-18 years) will be included in this study. No other vulnerable populations will be included.

11.0 Vulnerable Populations*

We will include children, and will not include pregnant women, and prisoners as they are not part of our usual patient population.

This study presents no more than minimal risk as it only requires use of VR-BF or computer application and completing questionnaires and interviews.

Study staff will discuss the study with the parents and children together, review the consent form with them, answer any questions, and obtain parental permission and assent from those children able to provide it.

12.0 Local Number of Subjects

Total number of subjects to be accrued locally: up to 102

We anticipate a $\geq 80\%$ recruitment and retention rate

13.0 Recruitment Methods

Patient Recruitment. Participants who are being managed by the Acute Postoperative Pain Service for the management of moderate to severe postoperative pain will be recruited continuously throughout the course of the study until enrollment numbers for each cohort are met. Once the family agrees that this is a study that they want to hear more about, a team member will describe the study procedures and verify eligibility criteria. Specifically, a team member will explain the study in greater detail and invite them to participate in the study. If the family is interested in proceeding to the consenting phase of the study, a team member will review the consent and assent in detail and cover all required elements of consent. The team member will answer any questions and verify understanding of the consent by asking questions about the study to the parent and child. The research coordinator will give the family adequate time to review the consent/assent form in full on their own. It will be made clear to the family that participation is

Feasibility and Acceptability of Technology-Based Interventions in the Perioperative Setting

completely voluntary, non-participation will not result in any consequences to them, and they are free to withdraw at any time for any reason.

Consenting/Assenting Procedures and Considerations. Due to needing subjects to begin study participation prior to surgery, we are requesting permission to consent by phone. Consent for participation will be done via an e-consent platform conducted through an application (REDCap) or another NCH supported application or with a paper informed consent form (ICF) provided ahead of time. A member of the study team will arrange for a time to discuss the study with the parent/LAR over the phone and answer any questions they may have about study participation. Informed consent will be documented by the person obtaining consent and parents/LAR will be asked to sign via the e-consent platform or if using the paper ICF, to bring the original version of the ICF with them to the training appointment. (see Section 12 for further detail). Subject/parent/guardian identity will be verified with documentation in EPIC.

Requirements. A signed consent form will be obtained from the participant. For participants who cannot consent for themselves, such as those below the legal age, a parent, legal guardian, or person with power of attorney, must sign the consent form; additionally, the participant's assent must also be obtained if he or she is able to understand the nature, significance, and risks/benefits associated with the study. The consent form will describe the purpose of the study, the procedures to be followed, and the risks and benefits of participation. A copy of the signed consent form will be given to the participant, parent, or legal guardian, and this fact will be documented in the participant's record.

Procedure. The approved, HIPAA compliant informed consent/assent will be provided to the study participant and the parents for review. The consent will be completed through the Research Electronic Data Capture (REDCap) database or on paper forms (if eConsent is unavailable at the time of consent). After allowing adequate time for review, the participant and parents will have the opportunity to ask questions and receive answers. When all questions have been answered, the consent and/or assent will be signed, and a signed copy will be provided to the participant and parents. This will all be conducted before any study measures interventions are undertaken.

Phone Consent. Due to needing subjects to begin study participation prior to surgery, we are requesting permission to consent by phone in order to have time to have subjects be trained on the technology prior to the scheduled surgery. Potential subjects may schedule surgery over the phone or at an in-person visit however subjects who are in person may not be available for approach due time constraints or already being overwhelmed with information regarding the surgery.

Documentation of Ineligibility. Screen failures will be documented on the source worksheets with the supporting data accompanying the eligibility screening form. Documentation of ineligibility or non-participation for each consented participant will be maintained in an electronic database (e.g., REDCap). Reports detailing the reasons for screen-failure and non-participation of eligible participants will be reviewed by the study team to determine if the exclusion criteria require revision in order to make the study accessible to families and study participants.

Payment. Patients may receive a stipend for participation, not to exceed a total of \$100 per patient. For time and inconvenience, the subject will receive up to \$100 - \$50 for completing all pre-surgery activities and an additional \$50 when the device is returned. There is no difference in how subjects will be compensated based on the phase of the study they are in.

Feasibility and Acceptability of Technology-Based Interventions in the Perioperative Setting

Subjects will be issued a debit card specially designed for clinical research. When a study visit is completed, funds will be approved and automatically loaded onto the card.

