In this scenario, the *Mindful Aurora* application would be used to deliver the VR content. This application acts as an escape for patients as well as a tool to help them learn slow breathing and relaxation techniques. It transports patients to an alpine meadow. With the help of a 10-minute relaxation narrative, study participants will observe the world transition from day to night while focusing on paced breathing. The goal of the application is to have participants mirror the rate of their breathing with the virtual world around them, which includes changes in floating butterflies and swaying trees to assist in the pacing of their breathing. This technique is effective in reducing respiratory rate, and consequently, increasing heartrate variability.^{20,97} This increased heartrate variability increases vagal tone, resulting in activation of the parasympathetic response and decreased pain.⁹⁷ This is the same application that has been used to deliver VR-BF content in **CCHMC IRB #2018-2892, 2019-1090, and 2020-0258.**

Manage My Pain. Control patients in Aim 2 will use the *Manage My Pain* application analogously to VR-BF per the protocol developed in Phase 1. This commercially available application is designed to assist patients with recognizing and reflecting on their pain and is highly engaging. It is available for iPhone, Android, and laptop download and is approved for children 12 years of age and older. In an assessment of commercially available pain applications, *Manage My Pain* was found to be appropriate for adolescents and had a high engagement score (4.2/5) as well as an excellent functionality rating (4.5/5).¹¹⁴ While it scored high overall (application quality score 4.06/5), it lacks the immersion and specific instruction in behavior change techniques,¹¹⁴ which are key features of VR-BF.

Device Tracking. Participants in Phase 1 as well as those randomized to the VR group in Aim 2 will receive a VR headset and FOREVR VR device to take home. During the first visit, these patients and families will be told that they will be given temporary possession of this equipment. To help increase our ability to retrieve these devices, they will be asked to sign a Device Agreement form. We will plan to collect the devices in the first postoperative clinic visit. If this is not possible, we will provide patients with a prepaid label and box to mail the device back to us. Other arrangements may be made with families for device retrieval as necessary.

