Research Design (Figure 3). Eligibility, recruitment, and study procedures will follow those described in Aim 1 but VR-BF or the control condition will be applied both pre- and

postoperatively according to the protocol refined in Phase 1. Figure 3 summarizes Aim 2 design. During the preoperative visit with our study team, patients randomized to the control group will download the *Manage My Pain* application onto their device. If patients do not have a personal device, we will ask a parent to download the program onto his or her phone or computer. We will provide explicit instructions on how to use the application and what features should be used. Patients will also be instructed on how to create a daily report documenting each day's use of the application prior to surgery. These daily reports will be returned to our study team. Like the VR-BF group, patients will receive scripted instruction on the benefits of mind body therapy, will be instructed to use the application for at least 10-minutes per day for seven days prior to surgery, and will be asked to complete a daily report using the application each day. On the day of surgery, a study team member will visit each participant to document possession of the FOREVR VR platform (intervention group), to collect reports, and to any answer questions.

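### Half of the stipend depends on returning a device that only the VR-BF arm receives, and no trigger is stated for controls, so post-discharge data completion could differ by arm.

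*Combined protocol and SAP*

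**What the plan says.** **Payment (Section 13.0, Payment).** The ceiling is set as follows: "Patients may receive a stipend for participation, not to exceed a total of" $100 per patient. It has two parts: $50 "for completing all pre-surgery activities and an additional" $50 "when the device is returned". On equality the section says: "There is no difference in how subjects will be compensated based on the phase of the study they are in". It does not mention study arm. On the payment card it says: "When a study visit is completed, funds will be approved and automatically loaded onto the card".

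**Who has a device (Section 6.0).** Under Device Tracking, Phase 1 participants and "those randomized to the VR group in Aim 2 will receive a VR headset and FOREVR VR device to take home". Collection is planned for the first postoperative clinic visit, with a prepaid box as the alternative. Under Aim 2, Research Design, "patients randomized to the control group will download the" *Manage My Pain* application onto their own device, or a parent downloads it.

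**What is measured (Section 6.0, Data Collection and Table 3; Section 17.0, Aim 2).** Retention is defined by "participation in the last study visit for both arms". Retention, adherence and burden each have an 80% benchmark in Table 3. Section 17.0 assesses feasibility and acceptability in each arm, and Section 2.0 requires both arms to be feasible and acceptable.

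**The concern.** In Phase 1 everyone has equipment to return, so the payment rule works. In Aim 2 only one arm does. After surgery a VR-BF family still has $50 to collect by a stated route, while a control family has no written payment left.

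In an efficacy trial this would be an administrative detail. Here, completion of the study and its measures is the outcome, and the results decide whether the control condition is carried into the efficacy trial. An incentive that differs by arm could make the control look more burdensome, or VR-BF look better completed, for a reason unrelated to either intervention.

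The rule also favours VR-BF data directly. VR-BF usage data are obtained from the device, so paying for its return helps secure them. Control usage comes from application reports that the family must hand over, and no payment is attached to those.

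**Working it through.** **1. Stipend by arm, read literally (Section 13.0).**
- Plan's total: $50 + $50 = $100, which matches the stated maximum.
- VR-BF: both triggers can be met, so the ceiling is $100.
- Control: only the pre-surgery trigger can be met, so the ceiling is $50. Half of the maximum (50/100) has no written trigger.

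**2. When the second payment falls due, against when each measure is taken (Section 6.0, Aim 2 Research Design and Device Tracking).**

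| Item | When collected | Exposed to the payment difference? |
|---|---|---|
| Patient questionnaire and interview | Final study visit, before discharge | Little; the device is due later |
| Home logs or reports | First postoperative clinic visit, or other arrangement | Yes, for patients who opt for home use |
| Home-use questions | First postoperative clinic visit, or other arrangement | Yes |
| Parent survey | Described alongside the clinic visit; timing not fixed | Probably |
| Retention | Last study visit | Only if that is the clinic visit |

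Home logs feed the burden measure. They can also feed postoperative adherence, which the Data Collection text defines as at least 5 of 7 daily sessions. Eligibility requires only one night in hospital, so for short stays the seven days run past discharge.

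**3. What one participant is worth (35 per arm, 80% benchmark).**
- 1/35 = 2.9 percentage points.
- 28/35 = 80.0%; 26/35 = 74.3%; 25/35 = 71.4%.

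**4. The plan's confidence-interval check (Section 17.0).** The plan asks whether the 95% interval contains 80%. Exact (Clopper-Pearson) intervals are:
- 28/35: 63.1% to 91.6%
- 26/35: 56.7% to 87.5%
- 25/35: 53.7% to 85.4%

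All contain 80%, as does every count from 23/35 (upper limit 80.9%) to 32/35 (lower limit 76.9%). Two or three extra drop-outs would therefore not change this check. They would change whether the point benchmark is met.

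**5. Sensitivity of the point benchmark.** The true rates below are assumptions; the documents give none by arm. The probability is P(X ≥ 28) with X ~ Binomial(35, p).

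| Assumed true rate, VR-BF / control | P(at least 28/35), VR-BF | P(at least 28/35), control | Pooled rate |
|---|---|---|---|
| 80% / 80% | 0.60 | 0.60 | 80% |
| 85% / 75% | 0.86 | 0.32 | 80% |
| 90% / 70% | 0.98 | 0.13 | 80% |

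A pooled rate would hide the imbalance in the last two rows. The table shows what a difference would do if it occurred. It is not evidence that the payment rule produces one.

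**The case against.** A reader might infer that the rule biases arm-level retention. The documents do not establish this. Section 6.0 places the final study visit before discharge, and the device comes back afterwards. On that reading retention is already counted when the payment falls due. The device may also be mailed, so the payment rewards returning equipment rather than attending a visit. This part of the objection stands, and it limits the point on retention to the case where the last study visit is the clinic visit.

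A reader might also infer that controls are refused the second $50. Nothing says so. The stipend is worded as a maximum that patients may receive, and the card-loading sentence refers to completed visits, which both arms have. Section 6.0 (Blinding) says the consent will not reveal the use of any device, so the device-return wording may be shorthand for a more general rule; the consent form is not available to check. This stands too, but it leaves two possibilities: controls are paid less, or staff apply an unwritten rule. Both call for a correction to the text.

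Other limits are fair. Home use is optional in both arms, no confirmatory testing is planned, and a missed retention benchmark leads only to a review of drop-out reasons, which might reveal a payment cause. Paying for the return of loaned equipment is also a defensible choice. None of this supplies a control-arm trigger or protects the post-discharge data.

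**Conclusion.** The point holds in a limited form. As written, half of the stipend has a trigger that only the VR-BF arm can meet in Aim 2, and the equality sentence covers phase, not arm. This could produce different completion by arm, mainly of post-discharge logs or reports, home-use questions and the parent survey. Those feed burden and, for short stays, postoperative adherence.

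The literal difference is $50 of $100. Its behavioural effect cannot be derived from the documents, and any number of extra control drop-outs is an assumption. The conclusion rests on the payment text being followed as written. It is worth correcting because the rule bears on the outcomes the trial exists to measure, and differential completion cannot be repaired after the data are collected.

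**What to change.** Before Phase 2 enrolment, amend Section 13.0 (Payment) so that the second $50 is payable in both arms at the same milestone: completion of the last study visit and return of logs or reports. If the sponsor wants to keep the leverage on equipment, add device return as a further condition for VR-BF. State explicitly that compensation does not differ by arm.

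In Section 6.0 (Data Collection, Retention), state whether the last study visit is the pre-discharge visit or the first postoperative clinic visit.

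**Cost.** A wording amendment, plus at most 35 × $50 = $1,750 if control payments were not budgeted. The sample size stays at 70. If device return is separated from payment, there is somewhat less leverage for recovering headsets; the Device Agreement and prepaid label remain.
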